4 RESEARCH QUESTION/AIM(S)

The purpose of the present study is to test whether theory and evidence-based alternative communication formats, targeting message specificity and previously identified psychosocial predictors of adherence, could improve the behavioural impact of existing alert systems, compared to the official messages sent in association with the UK AQIs.

Research questions

Primary questions:

1) What is the main effect of using behaviourally enhanced messages, compared to the currently used DAQI messages, to present the health advice associated with air quality notifications for a hypothetical high air pollution scenario on adherence intentions?

Prediction:

A) The behaviourally enhanced messages will lead to stronger intentions to adhere to recommendations.

2) What is the main effect of using a behaviourally enhanced message, compared to the currently used DAQI messages, to present the health advice associated with air quality notifications on actual behaviour changes at four weeks?

Prediction:

A) The enhanced messages will lead to greater behaviour changes.

3) In case of a real alert being issued during the study period, how do the different messages affect actual behaviour change?

Prediction:

A) The enhanced messages will lead to greater behaviour change.

Secondary questions:

4) If there is a format effect, which variables mediate the relationship between the information format and behaviour change?

5) Which factors are associated with greater behaviour change across all groups?

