5. METHODS

5.1 DESIGN

This is a randomised control trial using a 2-way factorial design, with target population (2 levels: general population vs. individuals with a pre-existing health condition) and message format (2 levels: usual message format vs. behaviourally enhanced messages) as between-factors. Participants will be randomised to either the usual message group or the enhanced message.

[figure not shown]

Figure 2 Study flow diagram

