5.3 SAMPLE

Inclusion criteria

Inclusion:

- Users of air alert systems managed by the ERG
- Age: > 18 years
- Working or living in Greater London.

Exclusion criteria

- younger than 18 years
- not working or living in Greater London
- no longer users of the air quality alert smartphone application.

Sampling

Sample size was calculated using the G*Power statistical power analysis (32), to give 80% power to detect a statistically significant difference in the main outcome measures at $\alpha=0.05$, if a small to medium effect size of $f=0.02$ or higher is observed (9), adjusting for one covariate. Given the possibility of dropout, we inflated the sample size by 20%, and aimed to achieve a minimum sample size of $n=240$.

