6. STATISTICAL ANALYSES

6.1 Quantitative data

ANCOVAs will be performed for all the intentions measures in relation to the high air pollution hypothetical scenario, adjusting for baseline measures collected about one month earlier (target population and intervention/control group entered as fixed factors). Both main and interaction effects will be tested. ANCOVAs will also be performed for the actual behaviour change at 4 weeks (with the intervention/control group entered as fixed factor). These latter analyses will also be ran in the subgroups of healthy and at-risk participants. Chi square tests will be performed to analyse differences in proportion of self-reported actual behaviour change between groups, in relation to a real moderate air pollution episode. A two-way MANOVA (1000 bootstraps) will test whether there are differences between groups (both main effects and interactions) in perceived susceptibility, worry, severity, perceived response efficacy, perception of time, self-efficacy, trust, clarity, credibility and perceived informed choice measures. Multiple linear regressions will be used to assess the associations between main predictor variables and self-reported behaviour change at 4 weeks. Mediations effects of predictor variables on significant behavioural changes will be tested using PROCESS macro (38).

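### Mediation is tested only on behaviour effects that reach significance, so the indirect-effect estimate that question 4 asks for will often be withheld if the true total effect is smaller than the apparent design effect

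*Combined protocol and SAP*

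**What the plan says.** The condition appears in two places in the combined protocol and SAP, so it looks deliberate.

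- Section 4, secondary question 4: "If there is a format effect, which variables mediate the relationship between the information format and behaviour change".
- Section 6.1: "Mediations effects of predictor variables on significant behavioural changes will be tested using PROCESS macro (38".

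The main test that opens the gate is described in section 6.1: "ANCOVAs will also be performed for the actual behaviour change at 4 weeks (with the intervention/control group entered as fixed factor".

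Two related analyses in section 6.1 carry no such condition. One compares the belief measures between groups: "A two-way MANOVA (1000 bootstraps) will test whether there are differences between groups (both main effects and interactions) in perceived susceptibility, worry, severity", followed by further measures. The other is a set of multiple linear regressions of 4-week behaviour on the main predictors. Neither yields an indirect effect.

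**The concern.** Making mediation depend on a significant total effect treats that significance as a precondition for an indirect effect. It is not one. When a belief carries the effect, the total effect is the product of two paths and is therefore small. Each path can be much larger than the product and easier to detect. A direct effect in the opposite direction can also cancel the total while the indirect path is intact.

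The messages were designed to move reflective motivation (section 2), and the examples in Table 3 target response efficacy and response costs. After a null behaviour result, the useful question is whether the beliefs failed to move, or moved without changing behaviour. An interval for each indirect effect bears on that question, and the plan would not produce one.

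**Working it through.** **Inputs from section 5.3.** Power and alpha: "to give 80% power to detect a statistically significant difference in the main outcome measures at $\alpha=0.05". Effect size: "if a small to medium effect size of $f=0.02$ or higher is observed (9), adjusting for one covariate". Inflation and target: "we inflated the sample size by 20%, and aimed to achieve a minimum sample size of $n=240". Section 5.1 gives two message arms: "Participants will be randomised to either the usual message group or the enhanced message". The allocation ratio is not stated; 1:1 is assumed.

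**Step 1: reproduce n=240.** For an ANCOVA with numerator df 1 and one covariate, power comes from the noncentral F with λ = f²N.

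- f=0.02 as printed needs N=19,625, or 19,625 × 1.2 = 23,550 after inflation. This does not reproduce 240.
- f=0.20 needs N=199, and 199 × 1.2 = 238.8, which is 239. This agrees with 240 to within rounding.

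The apparent design effect is therefore f=0.20, or d = 2f = 0.40. The printed 0.02 looks like a misprint, which is a separate point. Completers: 240 / 1.2 = 200.

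**Step 2: how often the gate opens on one 4-week behaviour test.**

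| True total effect | 200 analysed | 240 analysed |
|---|---|---|
| f=0.20 (d=0.40) | 80% | 87% |
| f=0.14 (d=0.28) | 51% | 59% |
| f=0.10 (d=0.20) | 29% | 34% |

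The f=0.10 row comes from section 2, which cites a meta-analysis giving r=.10 for specific against generic recommendations. With equal groups, d = 2r/√(1−r²) = 0.20/√0.99 = 0.20, so f = d/2 = 0.10. The gate is shut more often than open below about d=0.28 with 200 analysed, or about d=0.25 with 240. If a baseline covariate correlated 0.5 with the outcome (an assumption), the gate would open at d=0.20 in 37% of trials (200) or 43% (240).

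**Step 3: what the gate costs.** The documents give no path sizes, so these are assumed: a is the message effect on the belief in SD, b is the standardised belief-to-behaviour slope, and total = a×b + direct effect. Detection means that both paths are significant at 0.05; a Monte Carlo 95% interval for a×b gave nearly identical results. The figures are simulated with 200 completers.

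| a | b | Direct | Total (SD) | Detected, no gate | Detected, with gate |
|---|---|---|---|---|---|
| 0.3 | 0.3 | 0 | 0.09 | 57% | 8% |
| 0.4 | 0.3 | 0 | 0.12 | 79% | 12–14% |
| 0.5 | 0.4 | 0 | 0.20 | 94% | 29% |
| 0.5 | 0.5 | 0 | 0.25 | 94% | 42% |
| 0.4 | 0.3 | 0.28 | 0.40 | 77–79% | 64–66% |
| 0.8 | 0.5 | 0 | 0.40 | 100% | 83% |
| 0.4 | 0.3 | −0.12 | 0 | 79% | 4% |

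Ranges show the spread across independent simulation runs. The gate costs little when the total effect is at the design value. It costs most when a belief carries the whole effect and the total is small, or when a direct effect opposes the indirect one.

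**Step 4: does selection distort the mediated effect?** With a=0.4, b=0.3 and no direct effect, trials that pass the gate show a mean total effect of about 0.33 SD against a true 0.12. The mean a×b in the same trials is about 0.14 against 0.12. With the direct effect of 0.28 it is 0.12 against 0.12.

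**The case against.** - **Both links are already tested.** A reader might infer that a null behaviour result leaves the trial with nothing on mechanism. The documents do not support that: the MANOVA (message to belief) and the regressions (belief to behaviour) run regardless. This stands, and it narrows the point. The substitute is incomplete, however. Neither analysis gives a×b with an interval. No follow-up tests to the MANOVA are stated, and its list appears to cover response costs only through perception of time. The regressions are not said to adjust for arm.
- **The gate may usually be open.** A reader might infer that mediation would usually be skipped. At f=0.20 it would be run in about 80% of trials. Section 6.1 also refers to behavioural changes in the plural, so the alert items and subgroup analyses could open the gate too. This stands: how often mediation is skipped depends on the true effect. The r=.10 in section 2 points to a smaller effect, but it concerns specificity alone and the intervention adds psychosocial messages. Mediation models opened by other outcomes would themselves be chosen for significance.
- **Selection bias.** A reader might infer that gating seriously inflates the mediated effect. Step 4 shows that it hardly does under these assumptions. The total effect is larger in trials that pass, but its ANCOVA is planned whatever the result.
- **Removing the gate does not establish mechanism.** Table 4 places the beliefs in the final questionnaire, alongside a behaviour item that looks back over four weeks, and lists no baseline beliefs. This stands in full. The detection rates in step 3 assume the right causal order and no confounding of belief and behaviour.
- **It is a secondary question.** Asking what mediates an effect only once one is found is coherent, and no primary result is affected. That limits the weight of the point but does not justify withholding an estimate from data already collected.

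**Conclusion.** The point holds in a limited form. Section 6.1 and question 4 make mediation conditional on a significant behaviour effect, which an indirect effect does not require. On a single test with 200 completers, the indirect-effect estimate would be withheld in about 20% of trials at f=0.20 (100 − 80) and about 71% at f=0.10 (100 − 29). Under assumed paths of 0.4 and 0.3, detection falls from about 79% to 13% with no direct effect, and from about 78% to 65% at a total effect of 0.4 SD. What is lost is the formal indirect effect and its interval; evidence on the component links remains. The sizes rest on 1:1 allocation, 200 completers, a single mediator and path values that the documents do not supply.

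**What to change.** In section 6.1, fit the mediation model for the 4-week behaviour outcome whatever the p-value of the total effect. Name a short list of mediators in advance, including response efficacy and response costs, and report each indirect effect with a bootstrap 95% interval. Delete the word significant from the mediation sentence and the opening conditional clause from question 4.

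Label these results exploratory. State that beliefs are collected in the same final questionnaire as the retrospective behaviour item, with no baseline belief measures, so the order of cause and effect is not established.

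The cost is a change of wording and one model on data already being collected. The downside is one more exploratory analysis, with some multiplicity across mediators; a short list keeps that small.

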	Actual Behaviour change ^c	In response to receiving the air quality alert: 
 - I reduced length or level of my physical activity outdoors - I changed my travel route - I changed my exercise location - I changed the time when I travelled - I changed the time when I exercised outdoors - If you answered no, please report the reasons [text box].
	Medication adherence ^c	If you have lung problems: 
 - I used my preventer inhaler daily - I carried my reliever inhaler with me when going outdoors. - If you answered no, please report the reasons [text box].
Final Online Questionnaire – at 4 weeks	Behaviour change at 4 weeks ^b	- In the past 4 weeks, how often have you taken action to reduce exposure to air pollution, I response to hearing or reading an air quality forecast?
	Physical activity ^d	- To stay healthy, the NHS recommends at least 150 minutes of moderate physical activity (e.g. cycling, fast walking, swimming) every week (e.g. 30 minutes 5 days a week). Based on this, how physically active were you in the last week? ^e
	Action planning	
 - In the last 4 weeks, to reduce your exposure to air pollution, have you considered making permanent changes to your daily travel route or exercise place and time?^c - In the last 4 weeks, how often have you checked air quality information before doing physical activity outdoors?^b
	Worry ^a	Adapted from Witte et al. (34) 
 - The information received through the CityAir app made me worry about the possibility of suffering health effects from exposure to air pollution

	- The information received through the CityAir app made me nervous and tense about the possibility of suffering health effects from exposure to air pollution
Severity ^a	Adapted from Witte et al. (34)
	- Air pollution is a severe threat to my health
Conditional susceptibility ^f	- How likely do you think you are to suffer from health effects due to air pollution if you do not take any action to reduce exposure? - How likely do you think people of your same age and sex are to suffer from health effects due to air pollution if they do not take any action to reduce exposure?
Response efficacy ^a	Adapted from Witte et al. (34)
	- Following the health advice received through the CityAir app is effective in protecting me from exposure to air pollution

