Medication response efficacy ^a	If you have lung problems: - Taking my preventer medications daily is effective in helping me to control my asthma - Carrying my reliever medication with me is an effective way to protect my health
Self-efficacy ^a	Items adapted from Witte et al (34) and Rhode et al (35)
	- I am confident I would be able to follow the health advice received through the CityAir app, if I wanted to
Medication self-efficacy ^a	Items adapted from Witte et al (34) and Rhode et al (35)
	- If you have lung problems: I am confident I would be able to take my preventer inhaler every day , if I wanted to - I am confident I would be able to remember to carry my reliever inhaler with me during days of poor air quality, if I wanted to
Response costs ^a	- I do not have enough time to follow the health advice received through the CityAir app - Taking side roads makes my journey too long
Medication response costs ^a	If you have lung problems: - Using the preventer inhaler daily is not safe - Using the preventer inhaler daily makes me dependent on it
Unwanted consequences of intervention ^a	- In the last 4 weeks I stopped exercising altogether due to receiving alerts about poor air quality - In the last 4 weeks, I made an emergency /unplanned visit to A&E or visited my GP due to symptoms caused by air pollution
Sensory cue prevalence ^a	- I trust my own perception of air quality more than any official air quality alert
Credibility ^g	- Meyer's credibility index (36,37) (α=.67)
Clarity ^h	- Overall, how clear were the messages received?
Perceived informed choice ^a	- I received enough information to make an informed choice on how to reduce my exposure to air pollution
Intentions ^a to adopt protective behaviour in response to hypothetical, high air pollution alert	[After reading again the high air pollution hypothetical scenario and tailored advice] - I intend to follow the recommendations received with the air alert to reduce exposure to air pollution - I will avoid going outdoors - I intend to reduce length or level of my physical activity outdoors - I intend to change my travel route - I intend to change my exercise location - I intend to change the time when I travel - I intend to change the time when I exercise outdoors

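### The planned mediation analysis cannot tell whether beliefs led to the 4-week behaviour or followed from it, so it should not be reported as mechanism

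*Combined protocol and SAP*

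**What the plan says.** Secondary question 4 in section 4 asks: "If there is a format effect, which variables mediate the relationship between the information format and behaviour change". Section 6.1 answers it with one sentence: "Mediations effects of predictor variables on significant behavioural changes will be tested using PROCESS macro". It does not list the mediators. The sentence before it uses multiple regression to "assess the associations between main predictor variables and self-reported behaviour change at 4 weeks", so the predictors are presumably the belief and perception measures in Table 4.

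Table 4 in section 5.6 fixes the timing:

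- Worry, severity, conditional susceptibility, response efficacy, self-efficacy, response costs, sensory cue prevalence, credibility, clarity and perceived informed choice appear only under "Final Online Questionnaire – at 4 weeks".
- The behaviour outcome under the same heading asks "In the past 4 weeks, how often have you taken action to reduce exposure to air pollution".
- Behaviour after a real alert is asked during the alert period, before any belief item.
- The first questionnaire holds intentions, previous behaviour, planning, physical activity and symptoms, and none of these belief items.

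Section 6.1 sets no condition on time order, plans no check of the reverse direction and gives no caution on causal reading.

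**The concern.** A mediation model takes the direction from mediator to outcome as given. It will fit just as well if the message changes behaviour and behaviour then changes belief. Here nothing in the data can separate the two, because each belief is recorded once, in the same sitting as a behaviour report whose reference period has just ended.

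Reverse influence is easy to imagine for some items. Whether side roads lengthen a journey is something people learn by trying them. Response efficacy and self-efficacy are asked about the app's advice after four weeks in which it may have been used. It is less plausible for clarity and perceived informed choice, which ask about the messages themselves. Worry lies in between: "The information received through the CityAir app made me worry about the possibility of suffering health effects from exposure to air pollution" credits the information with the feeling, but is still answered with hindsight.

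At stake is the answer to question 4. The trial could name response efficacy or self-efficacy as the reason the enhanced messages work, and later messages could be built around a belief that was only a by-product.

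**Working it through.** The plan gives no figure to reproduce. The point rests on timing, so the sources are set side by side first. A calculation then shows how often the planned test could mislead.

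**Timing**

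| Measure | First questionnaire | Alert period | Week 4 |
|---|---|---|---|
| Belief and perception items | no | no | yes, once |
| Behaviour after a real alert | no | yes | no |
| 4-week behaviour | previous 4 weeks only | no | yes, looking back 4 weeks |
| Intentions | yes, after the scenario | no | yes, after the scenario again |

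No belief value precedes the behaviour it is meant to explain, and none can be used as a baseline.

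**Illustration: inputs**

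- n = 240 × 0.8 = 192, from the target of 240 and the 20% dropout allowance in section 5.3.
- Arm effect on behaviour d = 0.4 SD (assumed). It equals 2f at f = 0.20. The protocol prints f = 0.02, but 240 is reached from f = 0.20: 199 needed, and 199 × 1.2 = 239.
- Behaviour-to-belief coefficient r = 0, 0.3 or 0.5 (assumed; the documents give none).

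**Model**

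y = 0.4·arm + e and m = r·y + √(1 − r²)·e′, with e and e′ standard normal. Belief has no effect on behaviour, so the true indirect effect is zero. The analysis estimates a (arm on m) and b (m on y given arm) and tests a × b.

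**Closed-form check**

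- Path a has mean r × 0.4 and standard error 2/√192 = 0.144.
- Path b has mean r and standard error about √((1 − r²)/192).
- r = 0.3: a = 0.12 and z = 0.12/0.144 = 0.83, so the chance of passing 1.96 is P(Z > 1.13) = 13%. Path b has z = 0.3/0.069 = 4.4, so it is almost always significant.
- r = 0.5: a = 0.20 and z = 1.39, so P(Z > 0.57) = 28%. Path b has z = 0.5/0.0625 = 8.
- r = 0: both paths are significant by chance in 0.05 × 0.05 = 0.25% of trials.
- Apparent share mediated = (0.4r × r)/0.4 = r², which is 9% at r = 0.3 and 25% at r = 0.5. The true share is zero.

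**Simulation**

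With a 95% Monte Carlo interval for a × b, the false rate per mediator is about 14% at r = 0.3 and about 29% at r = 0.5, against about 0.2% at r = 0.

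**Sensitivity**

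- With unit-variance belief noise, SD(m given arm) = √(1 + r²). The same formula then gives z = 0.12/0.151 = 0.80, or 12%, at r = 0.3, and z = 0.20/0.161 = 1.24, or 24%, at r = 0.5.
- Restricting to trials with a significant arm effect, as section 6.1 implies, and analysing 240 gives about 15% and 39%.

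**The case against.** The strongest objection is that this is ordinary single-occasion measurement in a secondary analysis. Mediation is examined only if there is a format effect, the randomised comparisons are untouched, and a limitation could simply be disclosed. That stands as a limit on weight. It does not remove the point, because the plan contains no such disclosure and question 4 is worded as a question about mechanism.

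A reader might infer three stronger things, which the documents do not support:

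- **That the order is reversed.** Beliefs and the 4-week behaviour report come from one sitting; only the reference period of the behaviour item lies earlier. Some beliefs may have formed before the person acted. What can be said is that the order is unknown.
- **That some false mechanism is nearly certain because many beliefs will be tested.** Such a figure depends on how strongly the beliefs correlate and on how many are tested. The documents give neither, so only the per-mediator rate is offered.
- **That end-of-study intentions would cure the problem as the mediation outcome.** They are forward-looking and come after the belief items ("After reading again the high air pollution hypothetical scenario and tailored advice"), but they share the same sitting, and past behaviour can drive both beliefs and intentions. If it does, a false rate of about 3% to 23% per mediator remains under assumed coefficients. Adjusting for the first-questionnaire intention is not clean either: section 5.4.2 describes randomisation before the scenario is read and that intention is given. The documents do not say outright that the advice shown then differs by arm. If it does, the adjustment removes part of the effect being decomposed.

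First-questionnaire intentions do precede the 4-week behaviour and could in principle be a mediator. The plan treats them as a baseline covariate and does not name them as one.

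**Conclusion.** The point holds. Table 4 gives no way to order belief and behaviour, so the PROCESS analysis in section 6.1 can present a consequence of acting as a mechanism. That conclusion rests on the documents alone. The size is illustrative: about 14% of mediators at r = 0.3 and 29% at r = 0.5, against 0.2% at r = 0, assuming 192 analysed, d = 0.4 and behaviour driving belief with no return path. Across the variants shown, the rates run from 12% to 15% and from 24% to 39%. The calculation does not show that reverse influence occurs, only that the planned test would not reveal it. The effect of message format on intentions and on behaviour is not in question.

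**What to change.** Change the wording in three places:

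1. **Question 4 (section 4).** Ask which beliefs differ by message format and which are associated with behaviour, without asking which mediate.
2. **Section 6.1.** Report belief against 4-week behaviour as association only, under question 5. If PROCESS is still run, name the variables in advance, label the output exploratory, and state that belief and behaviour were measured together, so a mediator cannot be distinguished from a consequence.
3. **Causal statement on beliefs.** Keep the randomised comparison of beliefs between arms (the planned MANOVA) as the causal result on beliefs. It estimates the total effect of format on belief, including any part that passes through behaviour.

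Do not present end-of-study intentions as a repaired mediation outcome. If that model is run, it is exploratory too, with the first-questionnaire intention described as measured after randomisation and after the advice was read.

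This needs no new data and no change to the questionnaires. The price is that the trial gives up its claim to explain why behaviour changed.
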